## **3.1 General Design**

The Tiny Cargo, Big Deal! (TCBD) emergency department (ED)-based intervention is designed to promote correct and consistent use of a size-appropriate child passenger restraint system on every trip. We will test the precision prevention intervention with a randomized, adaptive trial design. Caregivers (parents and legal guardians) of children who seek care for non-critical illness and injury at the Ann & Robert H. Lurie Children's Hospital of Chicago Emergency Department

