## ***3.2 Allocation to Interventional Group***

After completing the baseline survey, all caregivers will be randomized into one of two groups: 1) TCBD intervention group, or 2) control group. Computerized, block randomization (block sizes from four to eight) will be applied to assign eligible caregivers to the TCBD intervention or control group in a 3:1 ratio. Blocks will be stratified by age groups related to child passenger safety recommendations (<2 years – rear-facing CRS, 2-4 years – forward-facing CRS, 5-10 years – booster seat) and the child passenger safety behavior that led to eligibility for study (not using the recommended restraint currently or planning a premature transition in the coming 6 months).

After the 6-month follow-up assessment, caregivers in the intervention group only who continue suboptimal CRS use will be re-randomized by computer in a 1:1 ratio to receive either the basic or enhanced intervention. The enhanced TCBD will include one additional motivational interviewing (MI) session by phone in Month 7/8 and one to two additional tailored text messages in Months 7-12 (total of 7 tailored tips during these months compared to 4 tailored tips for those in the basic TCBD). The extra text messages will be sent to those in the enhanced TCBD group until size-appropriate restraint use is observed. Caregivers receiving enhanced TCBD will be encouraged to obtain a free seat check with a certified child passenger safety technician (CPST) in the community. The primary outcomes (size-appropriate CRS use and CPaSS) will be assessed in-person at Months 6 and 12. The secondary outcome, the CPaSS trajectory, is a measure of correct and consistent restraint use in response to the intervention and will be assessed by scoring photographs submitted by caregivers (Months 1-5; 7-11).

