#### 5.1.2 Visit 2 –Monthly photo requests (over 12 months of study enrollment)

Over the course of the study, all study participants will receive 8 photo requests in months 1, 2, 3, 5, 7, 8, 10, and 11 via text message from the study that asks for them to send us back digital photographs of how their child usually travels in their vehicle. Participants can complete a total of 8 photo requests over the course of the study and will be paid for completing each of them. The CPaSS measure will be used to assess all digital photographs and incorporates elements of seating position, mode selection, CRS fit, and CRS use/misuse drawn from AAP Guidelines and standardized error severity scores for child restraints.

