## 6 Statistical Plan

### 6.1 Sample Size and Power Determination

Briefly, our calculations are based on two-sample comparisons between groups (e.g., control and TCBD) using results from our pilot study that assessed percent size-appropriate child passenger safety behaviors at 6-month follow-up (referred to as the “response rate” below). For analyses involving multiple time points, these calculations represent a conservative lower bound on the power that would only be achieved if the effective sample equals 1 observation per person (i.e. perfect within-individual correlation). For the calculations below we assume: a) 17% response rate among controls; b) 25% response rate among TCBD caregivers at 6 Month (with 75% of TCBD caregivers re-randomized); and c) only 80% of the target sample (n=204 controls and n=516 TCBD in the initial dichotomy) will be available for analysis at follow-up. Components (a) and (b) are based on pilot data where the control group received generic educational materials and outcomes were assessed at 6-months. Component (c) is a conservative correction for attrition. For Aim 2, we estimated power while accounting for uncertainty in the group sizes by simulating response and re-randomization patterns according to the above probabilities and testing for significant between-group differences; this process was repeated 10,000 times and the power was estimated as the percent of replications in which a between-group difference was identified. Binary Outcome: For the binary response case, if the observed response rate is at least 29.4% among those receiving enhanced TCBD, it can be reliably (>80% power) distinguished from a control response rate of 17%. Analogously, a response rate of at least 27.6% among basic intervention would be reliably (>80% power) distinguished from control. Converted to Cohen's  $h$ , both differences reflect small-to-medium effect sizes ( $h = 0.30$  and  $h = 0.26$ , respectively). Numeric Outcome (CPaSS): If the standardized mean difference (i.e. Cohen's  $D$ ) is  $>0.25$  (a small-to-medium effect size), we can reliably distinguish between control and basic TCBD conditions. Similarly, if  $D \geq 0.28$ , a small-to-medium effect size, we will have sufficient power (80%) to distinguish the control and enhanced TCBD conditions. Aim 2: Monte Carlo studies of linear latent trajectory models indicate that a medium level of heterogeneity among the slopes and/or intercepts of the trajectories can be reliably recovered (power  $> 80\%$ ) with a total sample size of  $n=200$ , with power exceeding 95% when the level of heterogeneity is high; given that our sample size soundly exceeds 200, we expect sufficient ability to determine the underlying characteristic trajectory types. Nevertheless, we further justify our sample size with a brief simulation study. Assuming a final sample size of 720, conservatively assuming individuals are only measured at an average of 25% of the 12 monthly assessments, we simulate data from a population with four equally likely trajectory types: consistently low, consistently high, linearly decreasing, and starting high then dropping off. Because we have no basis for estimating variability in the score, we assumed mean/variance equivalence, consistent with the Poisson distribution. Due to the time required to fit such models, we only completed 200 simulation replications, where we were able to correctly conclude (based on BIC) that there were four

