**Aim 2:** To use latent growth curve models to identify characteristic trajectories for the CPaSS observed in digital photographs over the 12 study months and assess for correlates of the trajectory types. We hypothesize that caregivers will have different CPaSS trajectories in response to the basic intervention, the enhanced intervention, and the control condition. We expect to identify at least four patterns of response. **Statistical Analysis:** We will determine 12-month CPaSS trajectory types using adaptations of finite mixture models for the case where the units are trajectories. We will define trajectory shapes through methods combining semiparametric regression modeling (e.g., generalized additive models), with latent class regression, using the R package flexmix. Following convention, we will use the Bayesian Information Criteria (BIC) to determine the appropriate number of latent classes, while also making practical considerations to avoid overfitting, such as not allowing overly small groups to be created, as in previous applied work. Using the posterior probability of class membership, we place individuals into trajectory groups and treat that grouping as the outcome in a subsequent multinomial regression model to determine correlates of class membership, including treatment group, caregiver race/ethnicity, and child age group. If substantial uncertainty in class membership is found, outcomes in the multinomial model will be weighted accordingly.

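### The CPaSS trajectory is described as a measure of consistent use, but its classes describe the level and shape of the mean score, and yes/no size-appropriate use is not analysed across photo occasions

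*Combined protocol and SAP*

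**What the plan says.** Section 3.1 describes the intervention as "designed to promote correct and consistent use of a size-appropriate child passenger restraint system on every trip". Section 3.2 assigns the consistency part of that goal to the secondary outcome: "The secondary outcome, the CPaSS trajectory, is a measure of correct and consistent restraint use in response to the intervention". Section 3.4.1 says the same.

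Section 6.2, Aim 2, defines trajectory shapes through "methods combining semiparametric regression modeling (e.g., generalized additive models), with latent class regression, using the R package flexmix". The number of classes is chosen by BIC, and at least four patterns are expected. Then: "Using the posterior probability of class membership, we place individuals into trajectory groups and treat that grouping as the outcome", in a multinomial model with treatment group among the correlates. If class membership is substantially uncertain, the outcomes are weighted.

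The simulation supporting Aim 2 in section 6.1 uses "four equally likely trajectory types: consistently low, consistently high, linearly decreasing, and starting high then dropping off". On the variance it says: "we assumed mean/variance equivalence, consistent with the Poisson distribution". On the amount of data it says: "Assuming a final sample size of 720, conservatively assuming individuals are only measured at an average of 25% of the 12 monthly assessments".

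On the data available, section 5.1.2 schedules 8 photo requests and says that the score "incorporates elements of seating position, mode selection, CRS fit, and CRS use/misuse". Section 2 says that both primary outcomes, including size-appropriate use, are assessed by direct observation and from photographs. Table 1 in section 3.3 lists the dichotomous outcome only at Months 6 and 12, and Aim 1 in section 6.2 tests it at 12 months.

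**The concern.** A caregiver who uses the right restraint on some rides and not on others, with no trend, differs from a caregiver with a steady middling score mainly in the spread of the scores, not in their mean. A model whose classes are mean curves has little to go on in telling these two apart, least of all with few scores each. The multinomial result by arm would then be read as evidence on consistency when it is evidence on level and trend. A shift from intermittent to steady use, which section 3.1 sets as the goal, could be diluted or partly reported as a change in trend.

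The more direct quantity is the share of observed occasions with a size-appropriate restraint. It can be built from what is already scored in each photo set, but no analysis in sections 6.1 or 6.2 uses the yes/no outcome in that way.

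**Working it through.** **1. The plan's own Aim 2 figure.** Section 6.1 reports that BIC chose four classes in 100% of 200 replications (n = 720, about 0.25 × 12 = 3 scores each, Poisson). The class means are not stated, so the figure can be checked only under assumed low/high means. With a Poisson mixture of cubic curves, four classes were chosen in 8 of 8 replicates for means 3/12, 5 of 8 for 2/8, 2 of 8 for 2/20 and 0 of 8 for 1/4. The 100% is attainable but depends on unstated means. None of the four simulated types is intermittent, so the exercise says nothing about recovering intermittent use.

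**2. Where the information lies.** Suppose scores are Poisson with mean *hi* when the right restraint is used and *lo* otherwise, and use is random on half of occasions. The mean is (lo + hi)/2 and the variance is (lo + hi)/2 + (hi − lo)²/4.
- lo = 2, hi = 8: mean 5, variance 5 + 9 = 14. A steady caregiver with mean 5 has variance 5.
- lo = 3, hi = 12: mean 7.5, variance 7.5 + 20.25 = 27.75, against 7.5.

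The means are equal and only the spread differs. Tying the variance to the mean leaves that difference unmodelled.

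**3. Freely fitted mixtures.** The population had five equally likely types: steady low, steady high, decline, steady middle, and intermittent at 50% with the same mean as steady middle. Settings: n = 720; 3 or 8 scores per caregiver on average; means 2/8 and 3/12; K = 2 to 6 by BIC; quadratic curves; 6 replicates per setting. The Youden index is the largest difference, over classes, between the share of intermittent and the share of steady-middle caregivers assigned to that class. Ranges are over the settings in each row.

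| Variance model | Scores | Youden | Intermittent in a trend class | Steady middle in a trend class | True decliners in a trend class |
|---|---|---|---|---|---|
| Poisson or common | 3 | 0.11–0.16 | 22–40% | 21–49% | 61–74% |
| Poisson or common | 8 | 0.12–0.15 | 26–31% | 11–16% | 86–93% |
| Class-specific | 3 | 0.16–0.22 | 11–16% | 17–28% | 35–59% |
| Class-specific | 8 | 0.53–0.76 | 3–7% | 6–9% | 67–89% |

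Under Poisson or common variance, separation stays poor at both data densities. At 3 scores, steady-middle caregivers land in trend classes about as often as intermittent ones, so that part is sparse-data misclassification and not specific to intermittency. At 8 scores the excess is specific: 15 to 16 percentage points within each setting.

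**4. What a per-occasion analysis would give.** Take the section 6.1 rates (17% and 25%) and analysed numbers (204 and 516), two-sided 0.05, and effective n = n × m/(1 + (m − 1) × ICC), with ICC assumed between 0.3 and 0.7.
- m = 1: power 0.65.
- m = 3: multiplier 3/2.4 = 1.25 to 3/1.6 = 1.875; power 0.75 to 0.90.
- m = 8: multiplier 8/5.9 = 1.36 to 8/3.1 = 2.58; power 0.78 to 0.97.

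This is power for a proportion averaged over months, which is a different estimand from Month 12 use. It assumes that the planning rates also apply to photo occasions.

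**5. What photos cannot give.** The one-sided 95% lower bound for a caregiver's true use rate is 0.05^(1/8) = 0.69 after 8 of 8 correct, and 0.05^(1/3) = 0.37 after 3 of 3. A caregiver with 80% use shows 3 of 3 with probability 0.8³ = 0.51 and 8 of 8 with probability 0.8⁸ = 0.17. The raw share correct on every scored occasion therefore depends on how many sets arrive.

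**The case against.** The strongest reply is that section 6.2 leaves the model open: BIC chooses the number of classes, shapes are semiparametric, no score distribution is fixed, and uncertain membership is weighted. The Poisson assumption belongs to the power simulation, where 25% is called conservative. This stands in part. A reader might infer that the classes cannot tell intermittent use from a trend, and the documents do not support that. True decliners were placed in a trend class 59 to 93% of the time in 11 of 12 settings (35% in the other). With class-specific variance and 8 scores, intermittent use was partly isolated. But section 6.2 specifies no such variance, and weighting for uncertainty among mean-curve classes does not create a class for intermittency.

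A reader might also force intermittent caregivers into the four types of section 6.1. With assumed means 8 and 2 and about 3 scores, that labels roughly 36% consistently high, 36% falling and 28% consistently low. The split is an artefact of having no middle class. With a steady class at mean 5 and 10 scores, about 62% go to the middle and only about a fifth to a trend. Likewise, 25% of caregivers always correct and all caregivers correct 25% of the time give the same single-visit rate but 25% against 0.4% (0.25⁴) correct on four of four occasions. That contrasts two assumed extremes and does not describe this trial.

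Nor do the photo sets record use on every trip. Section 3 asks for pictures of how the child normally rides, so each set is one prompted occasion. Finally, a bare count of correct occasions would ignore order and photo non-response, so the remedy must model month and missing sets. Section 6.2 already provides logistic mixed models for repeated data, so the gap is one unlisted analysis, not a missing method.

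**Conclusion.** The point holds in a limited form. The plan names consistency as part of what the secondary outcome measures, but the planned classes describe level and shape of the mean score. Under Poisson or common-variance classes, and at the roughly 3 scores per caregiver that section 6.1 assumes, they separate intermittent from steady intermediate use poorly (Youden 0.11 to 0.16) and can place some intermittent caregivers in trend classes. The yes/no outcome is not analysed across photo occasions, although section 2 says that photographs assess it and restraint mode is scored in each set.

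The sizes rest on assumed score means, an assumed mix of five types, polynomial curves in place of the planned semiparametric fit, and 6 replicates per setting, so they are ranges for illustration. It would go too far to say that consistency is measured nowhere: the survey items are not in the documents, and the finding covers only the analyses in sections 6.1 and 6.2. The Aim 1 comparison at Month 12 by randomised arm is not affected. This should be put right, but it concerns a secondary outcome.

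**What to change.** 1. In sections 3.2 and 3.4.1, describe the trajectory classes as the level and shape of CPaSS over time.
2. In section 6.2, add a secondary analysis of size-appropriate use (yes/no) at each scored photo occasion, by initial randomised arm, using a logistic GLMM or GEE with month in the model so that trend and intermittency are not confounded. Report the arm difference in the proportion of scored occasions with a size-appropriate restraint.
3. As a descriptive supplement from the GLMM, report the between-caregiver variance and the model-based share correct at a fixed number of occasions, so that the result does not depend on how many sets each caregiver returned.
4. Report photo non-response by arm and month, and state how it is handled.
5. State that the analysis concerns observed, prompted occasions and does not establish use on every trip.

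The cost is wording plus one extra secondary model. No new data, visits or participants are needed. The drawback is that the result depends on photo response, which may differ between arms.

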## Monthly photo requests:

- **\*\*See section 9 of IRB app, "supporting documents" for a document called, "Tips & tricks for taking your monthly photo"** --this document will be provided to all participants enrolled in part 2 of the study. The RA will review this document during the ED baseline visit with the participant.
- No matter which group caregivers are assigned into at the baseline visit, we will contact the study participant again starting in 1 month. A member of our study team will send them a photo request via text message. This text message will ask them to share photos of their child as they normally ride in their car.
- These photo requests will be sent to their best phone number. All photos of their child will be sent back to us by the parent/legal guardian.
- They will get requests to submit photos a total of 8 times while taking part in this study (over the next 12 months). We will be asked for these photos during months 1- 5, and Months 7-11 of the study.
- They will get these photo requests only on the days and during the times that they tell us they are able to get messages from us. To update the days and times that they are free to be contacted, caregivers can reach out to our team at by phone or email or text message
- The participant will have a 4 hour window of time to submit their photo requests each month with an additional 4 hour grace period. If a participant submits their photos during their window of time each month and the photos meet the necessary requirements (meaning the RA is able to visibly see all elements of the child sitting in the car seat, then the photos will be approved and the participant will earn \$5 that month. Participants can earn a total of \$40 if they complete all 8 photo requests during their specified window each month and the photos are approved. If the participant completes 4 months of photo submissions in a row, then they will hit a "streak" and will earn an additional \$5. They can hit a "streak" up to 2 times over the course of the study, so they can earn up to an additional \$10.
- Photo message response time (evaluate and response) from study staff will be 24-48 hours. Photo requests will not be sent if the staff are not available to respond during that time window.

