## **3.3 Study Measures**

Over the course of this study, participants will complete the following surveys: screen, baseline, 6- and 12-month survey. At the 6-month follow-up, the participants will also complete a brief health literacy assessment called the Newest Vital Sign.

The selected measures for the surveys are reliable, valid, and have been pilot tested in the study population. Measures will be assessed at screening, baseline and re-assessed at the 6- and 12-month follow-up visits. Assessments will be self-administered or RC facilitated on a study iPad in the ED and at in-person follow-up assessments (Months 6 and 12). Skip patterns will reduce administration time. Our team has found baseline assessment lasting 20 minutes to be feasible and acceptable to caregivers in the ED setting during pilot testing.

Table 1 illustrates survey measures for this study along with the frequency/timing of assessments.

Table 1: Measures	Assessment Month(s)
OUTCOMES	
Primary Outcome	
Size Appropriate Restraint Use (dichotomous)	6 and 12
Child Passenger Safety Score direct observation	6 and 12
Secondary Outcome	
Child Passenger Safety Score remote observation	ED/Baseline through 12
Exploratory Cost Measures	
Intervention Time (ED, Phone MI) for RA/Counselor	ED/Baseline and 2
Intervention Time (ED, Phone MI, texts, web app) for caregiver	ED/Baseline through 12
Material Costs - iPads, computers, maintenance	ED/Baseline through 12
Intervention Costs - Photograph review, texts, web app	ED/Baseline through 12
MODERATORS/MEDIATORS	
Caregiver Demographic Characteristics, reason for ED visit	ED/Baseline
Child Size	

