## 3.4 Study Endpoints

### 3.4.1 Primary Study Endpoint

The primary outcomes (size-appropriate CRS use and CPaSS) will be assessed in-person at Month 12. The secondary outcome, the CPaSS trajectory, is a measure of correct and consistent restraint use in response to the intervention and will be assessed by scoring photographs submitted by caregivers (Months 1-5; 7-11) and collected by the study team (Months 6 and 12). Photographs will be scored using the CPaSS tool by research team members blinded to the treatment group.

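### The CPaSS trajectory is defined from different data in Sections 3.2 and 3.4.1, and the Aim 2 simulation assumes 12 assessments where the schedule gives 8 or 10

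*Combined protocol and SAP*

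**What the plan says.** The same secondary outcome is described in four places.

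- Section 3.2: the trajectory "will be assessed by scoring photographs submitted by caregivers (Months 1-5; 7-11". Ten months are named, with nothing at Month 6 or 12.
- Section 3.4.1: it is assessed by "scoring photographs submitted by caregivers (Months 1-5; 7-11) and collected by the study team (Months 6 and 12". The section adds that scorers are blinded to treatment group.
- Section 3.3, Table 1: the secondary outcome is "Child Passenger Safety Score remote observation", timed from the ED/baseline visit through Month 12.
- Section 6.2, Aim 2: "We will determine 12-month CPaSS trajectory types using adaptations of finite mixture models". The data are digital photographs over 12 months. No list of months and no minimum number of scores is given. Caregivers are assigned to classes from posterior probabilities, and class is then regressed on treatment group and other correlates. Weighting applies only if class membership proves substantially uncertain.

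On the schedule, Section 5.1.2 says "all study participants will receive 8 photo requests in months 1, 2, 3, 5, 7, 8, 10, and 11". Section 3, under Monthly photo requests, says "They will get requests to submit photos a total of 8 times while taking part in this study", yet the same bullet names Months 1 to 5 and 7 to 11, which is ten months.

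On power, Section 6.1 simulates 720 caregivers, "conservatively assuming individuals are only measured at an average of 25% of the 12 monthly assessments". It reports that the four trajectory types were found by BIC in all 200 replications.

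**The concern.** Two things are unsettled. First, an analyst could defend at least three datasets for one secondary outcome: caregiver photographs only, those plus Months 6 and 12, or all of these plus baseline. Nothing in Section 6.2 stops the choice from being made after the results are seen.

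Second, the simulation that justifies Aim 2 rests on 12 possible occasions, which the request schedule does not deliver under either definition. The choice matters because photographs may be sparse. A caregiver with one score shows no change over time, so the data can say little about whether that caregiver belongs to a flat or a declining class. The comparison of arms in Aim 2 runs through those class assignments. Section 6.2 also promises that every randomised subject is analysed, but it does not say how a caregiver with no photo score enters the class-membership regression.

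**Working it through.** **Inputs.** 8 requests (5.1.2 and Section 3); ten named months (3.2); two further photograph occasions, Months 6 and 12 (3.4.1); 12 assessments, 25% average completion and N = 720 (6.1); 900 enrolled (4.2); 80% available at follow-up (6.1).

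**Step 1: the plan's own figures.** 900 × 0.80 = 720 = 204 + 516, so the simulation's N reproduces. The 100% recovery of four classes cannot be reproduced exactly, because the class means and fitted shapes are not given.

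**Step 2: maximum number of scores after baseline.** Under 3.2: 8. Under 3.4.1: 8 + 2 = 10. The simulation's 12 equals the months named in 3.4.1 (10 + 2), but two of the named months, 4 and 9, have no request in 5.1.2.

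**Step 3: share with at most one score.** Assume each of n occasions is completed independently with the same probability p. The documents state neither condition. Then P(0) = (1 − p)^n and P(≤1) = (1 − p)^n + n·p·(1 − p)^(n−1).

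| Basis | n | p | P(0) | P(≤1) | P(≤1) × 720 |
|---|---|---|---|---|---|
| Requests in 5.1.2, rate carried over | 8 | 0.25 | 10.0% | 36.7% | 264 |
| Months named in 3.2 | 10 | 0.25 | 5.6% | 24.4% | 176 |
| Simulation in 6.1 | 12 | 0.25 | 3.2% | 15.8% | 114 |

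First row: 0.75^8 + 8(0.25)(0.75^7) = 0.100 + 0.267 = 0.367.

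**Step 4: sensitivity for the 8 requests.**
- p = 0.40 gives 10.6%, and p = 0.50 gives 3.5%.
- Keeping the simulation's mean of 12 × 0.25 = 3 scores over 8 requests (p = 3/8 = 0.375) gives 13.5%.
- If completion clusters within caregivers (beta-binomial at p = 0.25, assumed intraclass correlation 0.1 to 0.3), the share is 44% to 53%.

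**Step 5: add Months 6 and 12 to the 8 requests.** With attendance v at each visit, independent of the rest, P(≤1) = P(0)·[(1 − v)² + 2v(1 − v)] + P(exactly 1)·(1 − v)².
- v = 0.80: 0.100 × (0.04 + 0.32) + 0.267 × 0.04 = 0.036 + 0.011 = 4.7%.
- Month 12 present for all 720 and Month 6 for an assumed 90%: 0.100 × 0.10 = 1.0%.
- v = 0.25, as if the simulation's rate also held at the visits: 24.4%.

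**Step 6: does the number of classes still come out?** As a plausibility check, a Poisson mixture with class-specific cubic log-means was fitted to N = 720 at 25% completion, choosing 1 to 5 classes by BIC, with 15 runs per setting. The low/high class means were assumed. For means 2/10 and 5/20 respectively, four classes were chosen in 14/15 and 12/15 runs on 12 months, 15/15 and 15/15 on 10 months, and 14/15 and 15/15 on the 8-request schedule.

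**The case against.** The strongest reply is that most of the text already points to the wider definition. Section 3.4.1 is the endpoint section, while 3.2 is about allocation and carries a shorter version of the same sentence. On that reading only wording needs correcting. The data may then be no sparser than simulated: 8 × 0.25 + 2 × 0.80 = 3.6 expected scores, against 3. This largely stands as an argument for which definition to adopt. It does not remove the conflict, and it does not make 12 occasions available.

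Four stronger readings are tempting, and the documents do not support them.

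- *That 37% follows from Section 3.2 and the plan's own completion rate.* It does not. The months in 3.2 give 24%, and the plan's rate on its own 12 occasions gives 16%. The 37% joins the requests of 5.1.2 to a rate that Section 6.1 calls conservative and applies elsewhere. Photo sets are also paid for, with streak bonuses.
- *That these caregivers have no trajectory.* A single score still enters the mixture likelihood and yields class probabilities. Only caregivers with no score contribute nothing. Section 6.2 allows weighting and Section 8.2 mentions possible multiple imputation, though both are conditional.
- *That Aim 2 would fail to find its classes.* Step 6 gives no sign of this under the assumed means. What is weakened is individual assignment. By how much cannot be derived, because no class means are stated.
- *That photo submission differs by arm.* TCBD caregivers receive more messages (about 5 to 6 a month against 3 to 4), so it is possible. But both arms get the same requests and payments, and no submission rate by arm is given.

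**Conclusion.** The inconsistency is established on the text alone: 3.2, 3.4.1 and Table 1 give three data sources for one secondary outcome, and 6.2 leaves the matter open. The mismatch between 12 simulated occasions and 8 or 10 scheduled ones is equally plain.

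The size of the effect is conditional. About 37% with at most one photo score, and 10% with none, holds only if 25% applies to each of the 8 requests, completion is independent and the 3.2 definition is used. Higher completion lowers the share sharply and clustering raises it. Including Months 6 and 12 brings it to about 5% at the assumed 80% attendance, but it helps much less if attendance at those visits is poor. The consequence is weakly determined class membership for some caregivers in a secondary analysis. Aim 1 is unaffected. The point should be corrected before analysis, but it does not threaten the trial.

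**What to change.** - Make 3.2, Table 1 and 6.2 agree with 3.4.1: the trajectory uses all scored monthly photographs plus the Month 6 and Month 12 photographs, scored with CPaSS-R by staff blinded to arm. Extend the blinding text in 8.2, which now covers only the monthly submissions, to these two occasions.
- Do not substitute direct-observation scores (CPaSS-D) from the check-ins. They are a primary outcome, and their scoring may not be blinded.
- State whether the baseline score is a covariate or a time point.
- Reconcile the number and months of photo requests across Section 3, 3.2, 3.4.1 and 5.1.2.
- Re-run the 6.1 simulation on the actual observation pattern, with class means stated, and restate its result.
- Make posterior-probability weighting the default in the class-membership regression, and report by arm how many caregivers have no score or one score.

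The cost is wording and analysis time. No new data are needed, provided the Month 6 and 12 photographs are collected as 3.4.1 says. One small downside is that those photographs are taken in a different setting from the monthly ones; a source indicator in the model can address this.
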